## **9.6 DATA MANAGEMENT**

Data for this study is stored using the secured Instant Health Data (IHD) platform (<https://www.bhei.com/product>). Access to the data is granted by password to trained, BI personnel only. Full details of the data management plan are documented in a separate NIS-Data Management and Review Plan (NIS-DMRP).

## **9.7 DATA ANALYSIS**

The statistical analysis of this study is summarized below. Full details of the statistical analysis will be documented in the SEAP, which will be finalized before the start of data analysis. The final study cohorts will be created using the IHD platform and all analyses will be performed using SAS software ( )

### **9.7.1 Definitions**

- Index date: Date of the first recorded claim for a qualifying prescription of an index medication as a new user.

- Follow-up: Starts from the day after the index date until the first qualifying event has been met (see [Table 2](#) and [3](#)).
- Look-back period: Patients are required to have at least 6 months of continuous registration in the database prior to initiation of an index medication. The look-back period is defined as 6 months prior to the index date and including the index date. The look-back period was specified to confirm new medication use (i.e. having a first prescription claim for empagliflozin or other oral non- incretin/non-SGLT2i-containing hypoglycaemic without use of these medications in the prior 6 months) and describe baseline parameters, such as prior medical history and medications.
- Grace period: 30 days in main analysis [[c18659315-02](#)] and 90 days [[R18-1760](#), [RRA-21430](#), [P20-07536](#)] in sensitivity analysis.

Table 2 Definitions for study end date

Reason for End of Study or censoring (earliest date of options below)	Definition for End Date
Acute pancreatitis event	Date of the first acute pancreatitis using ICD9 or ICD10 codes
Switch of index medication to another hypoglycaemic agent; see Table 3	Last date of known prescription coverage (date of last prescription fill plus days' supply minus one day) and a grace period equal to 30 days. Exposure time will not extend past the date of the first prescription claim for the newly prescribed agent*
Addition of incretin-based therapy (with continuation of index therapy)	Date of the prescription claim for the added incretin therapy
Addition of SGLT2i (with continuation of index therapy)	Date of the prescription claim for the added SGLT2i therapy
Addition of insulin (with continuation of index therapy)	Date of the prescription claim for the added insulin therapy
Addition of the within treatment line comparator index drug; see Table 3 (with continuation of index therapy)	Date of the prescription claim for the added treatment line comparator index drug
Discontinuation of index drug	Last date of known prescription coverage (date of last prescription fill plus days' supply minus one day) and a grace period equal to 30 days*
End of study data	Date of death#, Date of end of registration, Date of Study End

\*The last date of known coverage may also be extended further to account for overlap periods – when a prescription is refilled before the previous supply was considered exhausted. Gaps between coverage and prescription refills that are less than the duration of each patient's respective grace period will be considered continuous exposure time.

#It is not typically possible to ascertain all deaths that occur in studies based on administrative claims data.

Discontinuation, addition, and switching are defined in the SEAP. Considerations for the follow up time and censoring after switching or addition are presented in Table 3.

Index drug for the monotherapy are empagliflozin and metformin, for the dual therapy empagliflozin and SU, and for the triple therapy cohort empagliflozin and TZD.

Table 3 Considerations for switching or adding during the follow-up period

Treatment Line	Index Drug	Can Add (i.e. do not censor)	Cannot Add (i.e. censor at switch/addition)
Monotherapy	Empagliflozin	SU, TZD, and medications not mentioned in the next column	Metformin, incretins*, other SGLT2i, Insulin
	Metformin	SU, TZD, and medications not mentioned in the next column	Any SGLT2i, incretins*, Insulin
Dual Therapy	Empagliflozin	TZD, and medications not mentioned in the next column	SU, incretins*, other SGLT2i, Insulin
	SU	TZD, and medications not mentioned in the next column	Any SGLT2i, incretins*, Insulin
Triple Therapy	Empagliflozin	Medications not mentioned in the next column	TZD, incretins*, other SGLT2i, Insulin
	TZD	Medications not mentioned in the next column	Any SGLT2i, incretins*, Insulin

\*Incretins = DPP-4i or GLP-1 RA.

In the dual therapy and triple therapy cohorts, if patients discontinue or switch medications other than index medication (e.g. metformin in the dual therapy cohort, and SU or metformin in the triple therapy cohort) they will not be censored; however, in the sensitivity analysis, this will be assessed by censoring those patients. Definitions for discontinuation, switch, and addition are mentioned in the SEAP.

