Data analysis:	The index date in this study is defined as the date of the first recorded claim for a qualifying prescription as a new user. Patients are required to have at least 6 months of continuous registration in the database prior to initiation of empagliflozin or a comparator drug (the look-back period). The look-back period includes the index date. The main analyses of this study will utilize a modified As-Treated (AT) approach. Follow-up starts from the day after the index date until the first qualifying event has been met: 

• The earliest claim for acute pancreatitis

• Addition of or switch to an incretin-based therapy (DPP-4is or GLP-1 RA) or insulin

• Addition of or switch to the within treatment line comparator index drug (see section 9.7)

					

Name of company: Boehringer Ingelheim			
Name of finished medicinal product: Jardiance®			
Name of active ingredient: A10BK03 Empagliflozin			
Protocol date: 10/DEC/2021	Study number: 1245-0201	Version/Revision: 1.0	Version/Revision date: NA

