### **9.3.1 Exposures**

For this study, eligible patients will be identified from prescriptions/dispensings for the following study medications of interest (index medications):

Study drug will include:

- New therapy with empagliflozin (index medication) for the treatment of T2DM:
  - As monotherapy
  - As dual therapy (on a background of metformin)
  - As triple therapy (on a background of metformin and SU)

Comparator will be:

- New therapy with an oral non-incretin/non-SGLT2i-containing hypoglycaemic agent for the treatment of T2DM:
  - As monotherapy (metformin monotherapy): index medication is metformin
  - As dual therapy (SU on a background of metformin): index medication is SU
  - As triple therapy (TZD on a background of metformin and SU): index medication is TZD

This leads to the following comparisons:

- Monotherapy: Empagliflozin vs metformin
- Dual therapy: Empagliflozin vs SU, both on background of metformin
- Triple therapy: Empagliflozin vs TZD, both on a background of metformin and SU

Fixed-dose combinations will be considered equivalent to their free combination regimens. For instance, initiators of Synjardy will be categorized as dual therapy of empagliflozin. Combinations beyond triple therapy (i.e., use of 4+ glucose lowering drugs) will not be considered.

The index date is defined as the date of the first recorded claim for a qualifying prescription as a new user. Patients are required to have at least 6 months of continuous registration in the database prior to initiation of empagliflozin or a comparator drug (the look-back period). The look-back period was specified to confirm new medication use (i.e., having a first prescription claim for empagliflozin or other oral non-incretin/non-SGLT2i-containing glucose lowering drugs without use in the prior 6 months) and describe baseline parameters, such as prior medical history and medications. The look-back period includes the index date.

The study will be conducted utilizing a modified “as-treated” approach. Study follow-up will start the day after initiation of index medication and will continue until:

- The first occurrence of the outcome

- The date of end of continuous registration in the database
- The date of death
- The date of study end (31 October 2020)

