### **9.3.2      Outcomes**

#### **9.3.2.1      Primary outcomes**

In this study we will use a modified version of an algorithm developed and validated in the [REDACTED] with a sensitivity of 89.8% and a specificity of 79.4% [[R20-3555](#), [R20-3554](#)]. In the original algorithm, only the Logical Observation Identifiers Names and Codes (LOINC) were used for the lipase measurement but since these codes are only available for a subset of patients in Marketscan and Optum databases, to accommodate database needs, the equivalent Current Procedural Terminology (CPT) codes were added to the algorithm. This modified algorithm is:

- The presence of an acute pancreatitis diagnosis from any of the inpatient (not restricted to the primary diagnosis), outpatient, or emergency contacts diagnoses (ICD-9-CM 577.0 or ICD-10-CM K85)  
AND
- A lipase measure within +/- 7 days of the acute pancreatitis diagnosis (using LOINC code of 3040-3 and 2572-6 or CPT code of 83690 for lipase)  
AND
- An abdominal ultrasound (using CPT codes of 76700 and 76705) within +/- 7 days of the acute pancreatitis diagnosis

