### **9.7.3 Main analysis**

The study will be conducted utilizing a modified “as-treated” approach. Users of empagliflozin or a comparator oral non-incretin/non-SGLT2i-containing hypoglycaemic agent will be considered exposed from the date of first prescription claim until earliest claim for acute pancreatitis or until one of the following censoring criteria have been met (Table 3):

- The date of end of continuous registration in the database
- The date of death
- The date of study end
- The date of discontinuation of index medication (defined as the date of the last date of last dispensing + days supply + grace period). The grace period is a time period after exposure end during which observed outcomes are still attributed to the exposure. Grace

period varies according to the specific outcome. In this study, for acute pancreatitis, we have 30 days grace period in the main analysis [[c18659315-02](#)] and 90 days in the sensitivity analysis [[R18-1760](#), [RRA-21430](#), [P20-07536](#)].

- The date of switch of index medication to another hypoglycaemic agent
- The date of addition of incretin-based therapy (with continuation of index therapy)
- The date of addition of SGLT2i (with continuation of index therapy)
- The date of addition of insulin (with continuation of index therapy)
- The date of addition of the within treatment line comparator index drug (with continuation of index therapy)

For those who switch to an incretin therapy/SGLT2i, or switch to the within treatment line comparator, exposure duration will include the last date of known prescription coverage before the switch. For discontinuation of the index drug (with no prescription claim for a new hypoglycemic drug), exposure duration will include the last date of known prescription coverage (date of last prescription fill plus days' supply minus one day) and a grace period equal to 30 days. The last date of known coverage may also be extended further to account for overlap periods – when a prescription is refilled before the previous supply was considered exhausted. Gaps between coverage and prescription refills that are less than the duration of each patient's respective grace period will be considered continuous exposure time. For patients who switch, exposure time will not extend past the date of the first prescription claim for the newly prescribed switch agent.

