### **9.7.6 Sensitivity analysis**

At least the following sensitivity analyses will be performed:

1. All analyses will be performed using an alternate outcome definition using the primary hospitalization discharge diagnosis only (ICD-9-CM 577.0 or ICD-10-CM K85 acute pancreatitis).
2. Exclude cases with ICD-10 K85.2x (Biliary acute pancreatitis) and K85.3x (Alcohol induced acute pancreatitis) and also report the percentage of these cases in overall identified acute pancreatitis cases.
3. Implement an intention-to-treat approach, where all users maintain assignment to their original treatment arm throughout a fixed follow-up period 12 months after first exposure. Users of empagliflozin or a comparator oral non-incretin/non-SGLT2i-containing glucose lowering drugs will be considered exposed from the date of first prescription claim (following a 6-month period without a prescription claim for their index medication) until earliest claim for acute pancreatitis or until one of the following censoring criteria have been met: death, end of registration, or study end. In this analysis, patients discontinuing therapy will not be censored.
4. Subgroup analyses will be performed focusing on patients with and without history of eCVD in the 12 months prior to the index date
5. It is known that Diabetic ketoacidosis (DKA) can be complicated with pancreatitis. As a sensitivity analyses, cases with prior DKA will be excluded.
6. In dual or triple therapy cohorts when the non-index medication (metformin) is discontinued or switched patients will be censored.
7. Considering grace period of 90 days for all medications.

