6.2.3 Follow up

Follow up starts at the day after the index date until the first qualifying event has been met (see table 2 and 3 of the study protocol).

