7.1.3 Definition the censored follow-up end

The study will be conducted utilizing a modified “as-treated” approach. The follow up time starts from index date till the earliest date of these following events:

1. Discontinuation of index drug.
2. Switch or add-on the within treatment line comparator (other SGLT2 in empagliflozin group or the comparator group. Please refer to [Table 1](#) for different switch or add-on scenarios for each group.
3. Outcome: AP event. The first date of AP event is the event date.
4. The minimum date of death date or enrollment end date or study end date

As long as it is not the treatment line comparator, patients are allowed to add a non-incretin/non-SGLT2i hypoglycemic agent to their index therapy and can also switch to non-incretin/non-SGLT2i hypoglycemic agents.

Based on the feasibility studies, the patients having fixed dose of Empagliflozin + Metformin are defined as dual Empagliflozin patients. The index date is the first prescription of fixed dose prescription.

For the patients starting Metformin then Empagliflozin, these patients are free dose Empagliflozin + Metformin dual patients and they are defined as dual Empagliflozin patients by following exposure group definition process. The index date is the first Empagliflozin prescription date.

For both situations, the index drug is Empagliflozin. The censor date will be captured by following the same rule.

Proprietary confidential information © 2022 Boehringer Ingelheim International GmbH or one or more of its affiliated companies

Censoring Event as the End of Study Period

Only look for the **censor events** during the **first continuous exposure of index drug**.

The **discontinuation of index drug** is the end of **first continuous exposure of index drug**, which is the 30 days after the last days of supply.

Version of databases : Optum: Q1, 2021; [REDACTED] CCAE: Q3, 2020

08.2014

[figure not shown]

Figure 2

Diagram for definition of the censored end of follow up

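### The event that ends follow-up is defined two ways: by the full three-part outcome algorithm, and by the first pancreatitis code or claim

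*Protocol*

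**What the plan says.** The primary outcome in protocol section 9.3.2.1, repeated in the abstract, has three parts joined by AND: a diagnosis code from any setting, "A lipase measure within +/- 7 days of the acute pancreatitis diagnosis", and an abdominal ultrasound in the same window.

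The rules for ending follow-up use two kinds of wording.

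- **Code or claim.** Table 2 (protocol 9.7.1) has "Date of the first acute pancreatitis using ICD9 or ICD10 codes". Section 9.7.3 follows patients "until earliest claim for acute pancreatitis or until one of the following censoring criteria have been met". The abstract's list of follow-up ends begins with "The earliest claim for acute pancreatitis". The intention-to-treat analysis (9.7.6, item 3) has "until earliest claim for acute pancreatitis or until one of the following censoring criteria have been met: death, end of registration, or study end".
- **Outcome.** Protocol 9.3.1 has "The first occurrence of the outcome". SAP 7.1.3 has "Outcome: AP event. The first date of AP event is the event date", without defining the event there.

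The SAP points both ways. Its section 6.2.3 sends the reader to protocol Tables 2 and 3, 10.1 to protocol 9.7.1 and 10.3 to protocol 9.7.3. Its section 7.2 sends the reader to protocol 9.3.2. Neither document says how to treat a code that lacks the lipase test or the ultrasound.

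**The concern.** A programmer who follows Table 2 to the letter needs only a code, while one who follows 9.3.2.1 needs three components. The difference matters because protocol 9.9.3 warns that providers may use the pancreatitis code to rule the diagnosis out, and gives the algorithm as the safeguard.

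Taken literally, the code-or-claim wording allows two departures from the intended outcome:

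- An unconfirmed code could end follow-up, or supply the date for a later confirmed event. For example, a code in month 2 that fails the algorithm could become the recorded date of an episode confirmed in month 9.
- An unconfirmed code could be counted as the event. False events that occur equally in both groups pull the hazard ratio towards 1. Here the null hypothesis is a ratio of at least 1.5, so that pull favours concluding that 1.5 is excluded.

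Protocol 9.8 also requires two analysts to reach consistent results independently, which presupposes a single event rule.

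**Working it through.** **1. The wording side by side**

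| Place | What ends follow-up as the event |
|---|---|
| Protocol 9.3.2.1 (defines the outcome) | code + lipase + ultrasound |
| Protocol 9.3.1 | first occurrence of the outcome |
| SAP 7.1.3 | AP event, not defined there |
| Protocol 9.7.1, Table 2 | first ICD code |
| Protocol 9.7.3 | earliest claim |
| Protocol abstract, data analysis | earliest claim |
| Protocol 9.7.6, item 3 | earliest claim |

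**2. The plan's own figure**

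Inputs from protocol 9.5: rate 0.0022 in both groups, margin 1.5, one-sided alpha 0.05, power 80%, 1:1 allocation, 1 year of follow-up each.

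- The Farrington-Manning restricted estimates under the null are 0.001760 and 0.002640.
- Null variance: 0.002640 × (1 − 0.002640) + 1.5² × 0.001760 × (1 − 0.001760) = 0.006585.
- Alternative variance: (1 + 1.5²) × 0.0022 × 0.9978 = 0.007134.
- n = (1.645 × √0.006585 + 0.842 × √0.007134)² / (0.5 × 0.0022)². With unrounded values this is 34,585.4 per group, matching Table 1.
- Expected events: 2 × 34,585.4 × 0.0022 = 152.2.

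**3. If unconfirmed codes only end follow-up**

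Assumptions: 2.2 per 1000 person-years (PY) is the rate of algorithm-confirmed events. All codes together are m times as frequent, with m from 1.25 to 3. A patient cut off loses half a year on average.

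- Proportion cut off = 1 − exp(−0.0022 × (m − 1)): 0.055% at m = 1.25 and 0.44% at m = 3.
- PY lost = 69,170.8 × proportion × 0.5: 19 at m = 1.25 and 152 at m = 3.
- Confirmed events expected in that time at 2.2 per 1000 PY: 19 × 0.0022 = 0.04, up to 152 × 0.0022 = 0.33, out of 152.

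This is negligible for power.

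**4. If unconfirmed codes are counted as events**

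Assumptions: events meeting the algorithm are treated as true, false codes occur at the same rate in both groups, and confirmed events are held at 152.2. Let f be the share of counted comparator events that are false.

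- Observed HR when the true HR is 1.5: 1.5 × (1 − f) + f.
- Counted events, approximately: E = 152.2 / (1 − f).
- Chance of excluding 1.5 at one-sided 5% (Schoenfeld variance): Φ(ln(1.5 / observed HR) × √(E/4) − 1.645).

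| f | Counted events | Observed HR | Chance of wrongly excluding 1.5 |
|---|---|---|---|
| 0 | 152 | 1.50 | 5% |
| 0.1 | 169 | 1.45 | 8% |
| 0.2 | 190 | 1.40 | 12% |
| 0.3 | 217 | 1.35 | 19% |
| 0.5 | 304 | 1.25 | 48% |

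**The case against.** The best defence is that the outcome itself is not in doubt. Section 9.3.2.1 and the abstract state the algorithm in full. Section 9.3.1 and SAP 7.1.3 tie the end of follow-up to the outcome, and the Cox model in 9.7.3 uses time to the first acute pancreatitis event. Section 9.9.3 says the algorithm is there to mitigate rule-out coding. Item 1 of 9.7.6 treats a diagnosis-only definition as an alternate outcome, for sensitivity analysis.

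Table 2 can also be read as a dating rule. Its left column names the acute pancreatitis event and its right column gives the end date. Because the tests may fall up to 7 days either side of the diagnosis, a confirmed event needs one date, and the code date is a natural choice.

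Most of this stands. A reader might infer from Table 2 that unconfirmed codes will be counted or will stop follow-up. The documents do not support that: no text says a code alone suffices, and several places point the other way. A reader might also try to size the problem from the 79.4% specificity. The documents do not say in which patients it was measured, or what share of coded patients are true cases, so it cannot fix the number of unconfirmed codes.

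The defence does not remove the conflict. Even as a dating rule, Table 2 takes the first code rather than the first qualifying one, three other places use the earliest claim, and a code that fails the algorithm is left without a rule.

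**Conclusion.** The inconsistency is real and should be resolved, but it is a conflict of wording and not proof that the analysis will use a code-only event. The balance of the text favours the full algorithm.

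If unconfirmed codes merely ended follow-up, about 19 to 152 of 69,171 PY would be lost for m from 1.25 to 3. A reader might infer that this materially changes the primary hazard ratio, but nothing in the documents shows that it would.

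The consequence worth guarding against is counting such codes as events. With 10% to 50% false events in the comparator group, a true hazard ratio of 1.5 would read about 1.45 to 1.25, and the chance of wrongly excluding 1.5 would rise from 5% to between 8% and 48%. These are illustrations, resting on an assumed false share, false codes equally frequent in both groups, and 152 confirmed events. The planned 34,585.4 per group is not in error on this point.

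**What to change.** In Table 2 of protocol 9.7.1, in 9.7.3, in the abstract's follow-up rule and in item 3 of 9.7.6, replace the event wording with: *date of the first acute pancreatitis diagnosis code that meets the full 9.3.2.1 algorithm*. Add one sentence: *a code that does not meet the algorithm neither counts as an event nor ends follow-up*. Item 1 of 9.7.6 keeps its own alternate definition, and the text should say so.

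The cost is wording in four places, recorded as a protocol amendment as 9.8 requires. It needs no extra data and no change to the sample size.

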### 9.7.2 Propensity score approach

Decisions to begin a specific hypoglycaemic agent are influenced by demographic, medical, and clinical factors, and same factors might be associated with the outcomes of interest. The propensity score is the predicted probability of being assigned to a particular treatment conditional on a set of observed covariates. Because the models predict the probability of being treated with the exposure drug and not the probability of experiencing the outcome, a high number of variables can be used in the predicting regression model [[P12-04844](#), [R14-5241](#), [R14-5284](#), [R14-5389](#)].

Propensity scores for the comparison of empagliflozin vs. study comparator will be generated. Furthermore, given the different inclusion/exclusion criteria used for each treatment line cohort, the propensity scores will be cohort specific (i.e., propensity scores will be calculated for the monotherapy, dual therapy and triple therapy cohorts separately).

As a first step, a propensity score is estimated for each cohort member at the index date, based on the values of the observed covariates during the look-back period. In this study, propensity scores will be estimated by conducting multivariable logistic regression modelling and incorporating measured potential predictors of therapy as independent variables and exposure group status (empagliflozin group vs. comparator) as the outcome.

We will use PS matching to balance a number of covariates. Key advantages of PS matching are that large numbers of covariates can be adjusted even when studying infrequent outcomes, the achieved covariate balance can be documented, multiple outcomes can be studied after a single matching process, [R13-1120] and patients who cannot find comparable pairs will be implicitly dropped out of the analysis increasing the validity of findings [R17-1404].

The propensity score will be used to match patients in a 1:1 ratio using a nearest-neighbor algorithm and calipers of width equal to 0.2 of the standard deviation of the logit of the estimated propensity score [R13-3590, R18-2599, R16-1227]. A 1:n variable ratio matching will not be used as it involves several complications while providing only a minimal gain in estimation precision [R17-1267]. If balance is not achieved, the PS model will be refitted using interaction terms [R18-2599]. PS balance achievement will be inspected by tabulating all patient characteristics by treatment status and by assessing the standardized differences. Any patient characteristics with a standardized difference of >10% will be considered for additional post-matching adjustment [R13-3590].

With the publication of EMPA-REG OUTCOME trial results in September 2015 and the approval of a separate indication to reduce the risk of cardiovascular death in adults with T2DM and established cardiovascular disease by the US FDA in December 2016, the characteristics of patients initiating empagliflozin has likely changed during the study period. To account for patient characteristics changing over time, patients will be matched on the calendar quarter-year of initiation of the study medication. If we lose too many patients using this method, we may instead decide to match on year of initiation of index medication and then include calendar quarter-year variable in the PS model.

